## Columbia Suicide Severity Rating Scale (C-SSRS)

Suicidal ideation and behavior will be summarized according to suggestions made in the Columbia-Suicide Severity Rating Scale Scoring and Data Analysis Guide [5][5]. A positive response for suicidal ideation is counted when subjects respond "yes" to any one of the five suicidal ideation questions (Categories 1-5) on the C-SSRS (i.e. a score > 0 for suicidal ideation score). Serious suicidal ideation is a suicidal ideation score of 4 or 5. A positive response for suicidal behavior occurs when subjects answer "yes" to any one of the five suicidal behavior questions (Categories 6-10) on the C-SSRS (i.e. a score > 0 for suicidal behavior score). The number and percent of positive responses of Positive Ideation, Serious Ideation, and Positive Behavior will be tabulated overall and by PTSD+ participants and CSO participants for each time period. Lifetime serious suicidal ideation and positive behavior frequencies will be compared to cumulative frequencies at all timepoints throughout the study.

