4.1 Planned Duration of Study and Visit Windows

The active part of the study will take about 2 months for the dyads to complete. There are additional remote follow-up visits, 3 months and 6 months after the primary assessment. Total study participation will last about 8 months.

Screening may take place over a 1-month period; final confirmation of enrollment may be combined with the first Preparatory Session. Additional time between the first and second Preparatory Session will be allowed if necessary for medication tapering. For example, the maximum washout would be seven weeks for participants tapering off of fluoxetine plus one week for stabilization. Enrolled dyads will immediately enter the Active Group (N=10). Dyads will participate in two Preparatory Sessions, two day-long Experimental Sessions with MDMA-facilitated CBCT sessions, and Integrative Sessions following each Experimental Session in conjunction with CBCT.

The Experimental Sessions will last 6 to 8 hours and will be scheduled 3 weeks apart, with an intervening course of non-drug therapy. The non-drug psychotherapy includes two Preparatory Sessions prior to the first Experimental Session and five Integrative Sessions after each Experimental Session. Integrative Sessions will be conducted by telemedicine (video conferencing whenever possible, telephone if there are occasions when video conferencing is not technically possible) and will include both members of the dyad. The sessions will follow a combination of the MDMA-assisted psychotherapy manual and the CBCT manual, with each method modified as needed to combine the therapies. Any delay between visits would result in a corresponding extension of study duration.

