4.2.1 Inclusion Criteria

Inclusion Criteria for Participants with PTSD

Individuals eligible to be enrolled into this protocol are participants who:

- 1. Meet DSM-5 criteria for current PTSD with a duration of 6 months or longer
- 2. Satisfies diagnostic criteria for PTSD using the CAPS
- 3. Are at least 18 years old
- 4. If in ongoing psychotherapy at the time participants are recruited into the study, participants may continue to see their outside therapist during the course of the study. Participants must sign a release for the Clinical Investigators to communicate directly with their therapist. Participants may not change therapists, increase the frequency of therapy, or commence any new type of therapy until after the evaluation session, 3 months after the final Experimental Session. Participants who do not live within reasonable driving distance of the study site (equal to or less than an estimated 2-hour drive from the study site) must be registered with a therapist or health clinic in the area in which they live so they can call for support and evaluation if necessary
- 5. Are willing to refrain from taking any psychiatric medications during the study period, with the exception of gabapentin when prescribed for pain control. Individuals using opiates for pain management will be asked to decrease the dose or avoid taking their pain medication the morning of experimental sessions if possible. If the participant is on stimulants for ADHD at Baseline, they can continue to use them at the same dose and frequency as long as they discontinue 5 half-lives before each MDMA-assisted session and do not restart for 10 days after each MDMA administration. Any psychoactive drugs, including stimulants, will be tapered in an appropriate fashion to avoid withdrawal effects. Medications will only be discontinued after consultation with the prescribing physician
- 6. Agree that, for one week preceding the MDMA-assisted session will refrain from:
 - a. Taking any herbal supplement (except with prior approval of the research team)
 - b. Taking any nonprescription medications (with the exception of nonsteroidal anti-inflammatory drugs or acetaminophen unless with prior approval of the research team)
 - c. Taking any prescription medications (with the exception of birth control pills, thyroid hormones or other medications approved by the research team)

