	Wellbeing			calls		

Baseline = During 1-month screening period prior to enrollment day.

Midpoint = 2 weeks after 1st Experimental Session.

Primary Endpoint = 1 month post Visit 15.

LTFU 3, 6 = 3 months and 6 months after Visit 15.

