## 6.0 Analyses

In general, nominal variables will be described in terms of frequencies and percentages and analyzed using chi square analysis. Ordinal and non-normal continuous variables will be described using sample median and range, and analyzed by non-parametric statistical tests, and approximately normal variables will be described using sample mean and standard deviations and analyzed by parametric statistical tests. All statistical tests will be two-sided and a difference resulting in a p-value of less than or equal to 0.05 will be considered statistically significant. All p-values will be rounded to and displayed in four decimals. P-value less than 0.0001 will be shown in tables as <0.0001. For any analysis that is called out as parametric, e.g. t-test, the parametric assumptions will be examined. If necessary, nonparametric analyses will be utilized, e.g. Wilcoxon rank-sum test.

Clinical data will be presented in tabular format. Data not subject to analysis according to this plan will not appear in any tables or graphs but will be included in the data listings. Analyses will be carried out with SAS Version 9.4 (or higher). Selected results may be presented graphically using standard graphical software.

Post-hoc exploratory analyses not identified in this SAP may be performed to further examine the study data. These analyses will be clearly identified as such in the final clinical study report.

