#### **Baseline Values**

Baseline values are from screening/baseline visit for all measures, except CAPS-5 and C-SSRS. Baseline CAPS-5 will be assessed, during screening (pre-study), no more than 8 weeks before the first experimental session. This allows adequate washout of at least five half-lives of pre-study psychiatric medications and active metabolites, plus one week for stabilization. If CAPS-5 is completed outside of this window for a participant, the PI will consult the CRA and Medical Monitor to determine if the Baseline CAPS should be repeated. For C-SSRS, pre-enrollment scores will be used as a measure of 'lifetime' suicidal ideation and behavior, and preparatory session 2 (visit 2) prior to drug administration will used as 'baseline.' If a subject was not administered the C-SSRS at preparatory session 2 (visit 2), then 'baseline' scores will be visit 3 pre-drug C-SSRS observation.

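### The only before-versus-during C-SSRS comparison sets lifetime history against about 8 study months, and the pre-drug baseline that the SAP defines is used in no stated comparison

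*SAP*

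**What the plan says.** The C-SSRS section of the SAP plans two things. First, it tabulates the number and percent with positive ideation, serious ideation (score 4 or 5) and positive behavior, overall and by role, for each period. Second, "Lifetime serious suicidal ideation and positive behavior frequencies will be compared to cumulative frequencies at all timepoints throughout the study".

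The SAP's Baseline Values section separates two reference points. For the lifetime measure, "pre-enrollment scores will be used as a measure of 'lifetime' suicidal ideation and behavior". For the pre-drug reference, "preparatory session 2 (visit 2) prior to drug administration will used as" baseline, with the Visit 3 pre-drug assessment as the fallback. The C-SSRS section never refers to that baseline.

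On duration, Protocol section 4.1 says that "Total study participation will last about 8 months". Protocol section 12.0 adds one further C-SSRS comparison, between PTSD+ and CSO participants.

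**The concern.** A before-versus-during comparison informs about treatment only if the two sides have similar opportunity to record an event. Here one side is a whole life up to enrolment and the other is less than a year. Nothing in the SAP adjusts for this. A drop from lifetime to on-study frequency could be read as reassurance when it mostly reflects the shorter window.

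Entry criteria push the same way. Protocol section 4.2.2 excludes current serious suicide risk but allows past attempts, so the lifetime column can hold events of a kind that participants were selected not to be at risk of on entry.

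The SAP already defines a more suitable reference point, Visit 2, and then leaves it unused. Suicidality is a named safety objective in a study that withdraws psychiatric medication and gives MDMA to both members of each dyad, so the C-SSRS summary should be able to show change within a person.

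**Working it through.** **The study window.** Protocol section 4.1 says that "The active part of the study will take about 2 months for the dyads to complete", and the notes to Table 4 give "LTFU 3, 6 = 3 months and 6 months after Visit 15". So 2 + 6 = 8 months, which reproduces the stated total. Section 4.1 also counts the follow-up visits from the primary assessment, which would give 2 + 1 + 6 = 9 months; this is checked below.

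**The lifetime window.** The inclusion criterion is "Are at least 18 years old", with no upper age limit. The documents give neither a lifetime C-SSRS rate nor years at risk. Assumptions: lifetime rate L from 10% to 70%, and years at risk Y from 5 to 30.

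**Expected on-study rate if risk is unchanged.** Under a constant hazard, p = 1 − (1 − L)^((8/12)/Y). For L = 50% and Y = 20, p = 1 − 0.5^0.0333 = 2.28%. Each cell gives p, then the ratio L/p.

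| L | Y = 5 | Y = 10 | Y = 20 | Y = 30 |
|---|---|---|---|---|
| 10% | 1.39%, 7.2 | 0.70%, 14.3 | 0.35%, 28.5 | 0.23%, 42.8 |
| 30% | 4.64%, 6.5 | 2.35%, 12.8 | 1.18%, 25.4 | 0.79%, 38.0 |
| 50% | 8.83%, 5.7 | 4.52%, 11.1 | 2.28%, 21.9 | 1.53%, 32.7 |
| 70% | 14.83%, 4.7 | 7.71%, 9.1 | 3.93%, 17.8 | 2.64%, 26.5 |

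The ratio runs from 4.7 to 42.8, an apparent fall of 79% (1 − 1/4.7) to 98% (1 − 1/42.8) with no change in risk. With Y = 8/12 year, so that the windows match, the ratio is 1.0 for every L. With a 9-month window the extremes become 4.2 (L = 70%, Y = 5: 1 − 0.3^0.15 = 16.5%) and 38.0 (L = 10%, Y = 30: 1 − 0.9^0.025 = 0.263%), so the choice of 8 or 9 months does not matter.

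**How much harm the comparison could absorb.** For the two columns to be equal, the on-study hazard would have to be Y/(8/12) times the lifetime average: 7.5 times for Y = 5, 15 for Y = 10, 30 for Y = 20 and 45 for Y = 30. With L = 50% and Y = 20, a fivefold rise gives p = 1 − 0.5^(5 × 0.0333) = 10.9%. Among 10 PTSD+ participants, 5 would be expected to be lifetime positive, and the binomial chance of fewer than 5 on-study positives is 99.8%.

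**What the per-period counts can show.** They are marginal totals. If 2 of 10 are positive at Visit 2 and 2 of 10 at Visit 16, these may be the same two people, or two who resolved and two new cases. A move from ideation category 1 to 3 stays inside positive ideation and never reaches serious ideation, so it changes no count.

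**The case against.** Several points on the other side stand.

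- A reader might infer that this is the only C-SSRS comparison, or the main one. Protocol section 12.0 also compares PTSD+ with CSO participants, and the SAP does not rank the lifetime contrast above its other summaries. The between-role comparison, however, says nothing about change under treatment.
- A reader might infer that the plan could hide emergent suicidality altogether. It could not. Protocol section 7.2.1 routes treatment-emergent, clinically significant ideation scored 4 or 5, or any behavior, into adverse event collection. Section 8.5 collects psychiatric adverse events throughout, and the SAP makes treatment-emergent adverse events its primary safety measure. Lesser worsening, in categories 1 to 3, depends mainly on the C-SSRS tables.
- Per-period counts let a reader set Visit 2 beside later visits. This is a partial remedy, for the reason shown above.
- A reader might infer that a chi-square test will be applied. SAP section 6.0 says that "nominal variables will be described in terms of frequencies and percentages and analyzed using chi square analysis", but as a general rule; the C-SSRS section names no test and no p-value. Only if that rule were applied would the problem arise that the same people are in both columns.
- The hazard model is crude. Participants have current PTSD, so present risk may exceed the lifetime average. Table 3 with its footnote G gives about 15 on-study administrations per person against one lifetime interview, which raises detection on study.
- The SAP follows a published scoring guide that cannot be checked here and might add baseline-shift outputs. The SAP's own text commits to none.

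**Conclusion.** The point holds as a defect in analysis and reporting. The only before-versus-during C-SSRS comparison in either document is biased toward reassurance by unequal windows, and the pre-drug baseline that would serve better is used in no stated comparison. The direction is strongly expected but not guaranteed. The size, about 5 to 43 times, is an illustration that rests on constant hazard and on assumed lifetime rates and years at risk. A claim that any fall must exceed 90% is not supported: the low end of the range is about 79%, and higher current risk or better detection could reduce it further. In a 10-dyad open-label pilot with separate adverse event reporting, this calls for a correction to the SAP and does not question the safety monitoring.

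**What to change.** 1. Delete the lifetime-versus-cumulative comparison. Report lifetime ideation and behavior among the baseline characteristics, as history only.
2. Add one shift table for the Safety population, by role and counting participants rather than responses: highest ideation category and any behavior after first dose against the Visit 2 baseline (Visit 3 pre-dose if missing), with the number and percent new or worsened.
3. Visit 2 is assessed after medication washout (Table 3, footnote F), so list ideation or behavior recorded there separately. Otherwise events that emerge during the taper disappear into the baseline.
4. Keep the table descriptive. If a p-value is given, use an exact paired (McNemar) test and state its very low power. With 10 per role, five discordant participants all in one direction give 2 × 0.5^5 = 0.0625; six are needed (2 × 0.5^6 = 0.031).

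The new contrast is not symmetric either. Of the roughly 15 administrations, about 13 follow the first dose (15 less Visit 2 and the Visit 3 pre-dose assessment), so it will tend to pick up cases. For a safety table that is the more cautious direction, and a further reason not to test it.

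The cost is one SAP sentence and one table. No new data are needed.

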## Subjective Units of Distress (SUD) and Vital Signs

SUD scores will be calculated including frequencies and percentages in the total sample and by PTSD+ participants and CSO participants at experimental treatment 1 (visit 3) and experimental treatment 2 (visit 10). Vital signs include heart rate, body temperature, systolic and diastolic blood pressure, and will be summarized using descriptive statistics at baseline and at each post-baseline time point. Systolic and diastolic blood pressure, heart rate, and body temperature readings above the pre-determined cutoff will be reported using numbers and percentages by timepoint.

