Cardiovascular effects will be assessed via blood pressure and pulse measurement. Blood pressure, body temperature, and pulse will be measured at the outset of the Experimental Session, once prior to administration of the supplemental dose, and at the end of the Experimental Session, or until it returns to near baseline levels. The timing of these measurements will be adjusted so they do not interfere with the therapeutic process. Blood pressure will be measured more frequently if there are symptoms, such as chest pain, shortness of breath or neurological symptoms or any other signs or symptoms that may be indicative of a medical complication.

A 100-millimeter visual analog scale will be used to assess changes in symptoms of preexisting tinnitus and/or chronic pain [173-175]. The Changes in Tinnitus and/or Pain visual analog scale will allow rating of symptom severity from "None" to "Worst Case Imaginable". This exploratory measure will enable quantification of subjective somatic symptoms that are known to be associated with PTSD [174, 176-178]. Presence of chronic pain is associated with PTSD, possibly as a result of psychological response to traumatic stress as reflected in brain activity, such as increased amygdalar activity in response to pain and transmitter systems involved in the stress response [174, 177, 178]. Both the PTSD+ participant and the CSO participant will be evaluated for Somatic Symptoms.

All AEs and spontaneously reported reactions will be collected, as described in Section 8.5. AEs and spontaneously reported reactions may be collected during face-to-face visits or over the telephone. Common reactions that are spontaneously reported are collected for seven days after each Experimental Session on a separate CRF page and will be categorized as mild, moderate, or severe. The researchers will ask participants about thoughts about killing or harming themselves at these visits and during the second and seventh day of telephone contact with the study therapists.

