5.2.4 Experimental Sessions (Visits 3 and 10 - Overnight Stay)

(Day 1 and approximately 3 weeks later)

CBCT Manual Sessions 4 and 5 practice (Visit 3) and Review (Visit 10)

Sessions 4 and 5 – Satisfaction enhancement and undermining avoidance. Specific content related to listening and approaching, and sharing of thoughts and feelings.

Table 5. Schedule of Procedures for Experimental Sessions

Approximate Time	Procedure or Action		
9:00	Urine drug screen and pregnancy test, participant acclimated to		
	environment, C-SSRS		
9:45	Baseline BP, BT, Pulse, SUD		
10:00	MDMA Administration, Begin video recording		
11:00	SUD		
11:30	BP, BT, SUD, Pulse, Administer optional supplemental dose		
12:30	SUD		
14:00	SUD		
As needed	BP, BT, Pulse		
Every 60-90 minutes	SUD		
Approximately six hours	C-SSRS, General Wellbeing, BP, BT, Pulse		
after drug administration			

Page 46 of 89

The PTSD+ participant and CSO participant will receive two Experimental Sessions of open-label MDMA-assisted psychotherapy in conjunction with CBCT scheduled three weeks apart. Procedures for MDMA-assisted psychotherapy in conjunction with CBCT will remain the same across all sessions, and all procedures will be the same.

Pre-drug:

- a. On the day of the Experimental Session, the PTSD+ participant and CSO participant will arrive approximately 60 to 90 minutes prior to drug administration.
- b. Confirm continuing eligibility by reviewing Inclusion and Exclusion Criteria including medications and adverse events.
- c. Perform a urine drug screen. A positive drug screen will be reviewed by the Clinical Investigator and may be cause for delaying drug administration to a later time, rescheduling the session to a later date, or withdrawing the participant from the study.
- d. If a participant is of childbearing potential, perform a urine pregnancy test. A positive pregnancy screen is cause for withdrawal from the protocol.
- e. If the dyad continues to meet criteria and the dyad reports that they followed appropriate rules and restrictions, the session will proceed.
- f. Review procedures for the Experimental Session with the dyad.
- g. Record the entire session to video and audio. Dyads will be given access to review audio or video recordings of their Experimental Sessions upon request.
- h. The session will last for approximately eight hours or longer, followed by an overnight stay at the study site.
- i. The therapists will administer the C-SSRS to the dyad prior to drug administration.

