7.2.2 Cardiovascular and Sympathomimetic Effects

The highest dose to be employed in this study, the active dose of 100 mg, followed by a supplemental dose of 50 mg after 1.5 to 2.0 hours, is expected to produce significant but transient, self-limited increases in blood pressure and heart rate. These changes should last no more than six hours. In less than 5% of volunteers in Phase 1 studies, peak blood pressure values were higher than 140/90 mmHg. Clinical intervention was not required in any of these cases. Nonetheless, careful monitoring of participants and predefined contingency plans will allow the researchers to rapidly identify and manage any related toxicity. For more information, see the sponsor's Investigator Brochure.

Risks posed by elevated blood pressure will be addressed by excluding people with preexisting hypertension and monitoring blood pressure and pulse, as described in Section 5.1.2. During Experimental Sessions the co-therapists will continually evaluate the patient for signs or symptoms of a developing hypertensive or other cardiovascular emergency. Participants reporting chest pain, shortness of breath or neurological symptoms or other potential indicators of hypertensive emergency or any other serious medical problem will have more frequent measurements and assessment by the study physician. Any participant who experiences medical complications during an Experimental Session will not be given another Experimental Session unless it is approved by the Clinical Investigator, study physician and the Medical Monitor. In case of need, participants will be transferred to the emergency room at the closest hospital, as described in Section 8.4. Reasons for moving a patient to an Emergency Department (ED) would include, but not be limited to, severe headache in the setting of hypertension, angina, or neurological deficits regardless of blood pressure. The Clinical Investigators and study physician may, at any time, make a clinical judgment to transfer the patient to the ED for closer monitoring and additional treatment.

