7.2.4 Body Temperature

MDMA administered in a controlled setting produces only a slight increase in body temperature [15] and ambient temperature does not enhance or attenuate this slight elevation in humans.

If temperature rises more than 1°C, attempts will be made to lower it by removing blankets and layers of clothing, decreasing the ambient temperature and, if necessary, directing a fan toward the participant. If at any time the temperature rises more than 1.5°C above Baseline despite these efforts, the study physician will be consulted for further evaluation and treatment

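### The SAP tabulates vital-sign exceedances by timepoint against an unstated cutoff and plans no count of participants who ever exceeded it

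*SAP*

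**What the plan says.** The SAP's vital-signs paragraph (section 6, Safety Analyses) contains two rules. Heart rate, temperature and systolic and diastolic pressure "will be summarized using descriptive statistics at baseline and at each post-baseline time point". Exceedances are handled separately: "Systolic and diastolic blood pressure, heart rate, and body temperature readings above the pre-determined cutoff will be reported using numbers and percentages by timepoint". No cutoff value, denominator, or rule for unscheduled readings follows, and no maximum is planned. Protocol section 12.0 adds only that vital signs will be examined and compared between PTSD+ and CSO participants.

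Protocol section 5.1.2 has blood pressure, temperature and pulse taken at the outset of each Experimental Session, "once prior to administration of the supplemental dose, and at the end of the Experimental Session". Table 5 in section 5.2.4 puts the first post-dose set at 11:30, after dosing at 10:00. It puts another about six hours after dosing, in the row reading "C-SSRS, General Wellbeing, BP, BT, Pulse". Between these, vital signs are taken as needed, and Table 5 gives that its own row.

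The extra readings follow suspected trouble. Section 5.1.2 states: "Blood pressure will be measured more frequently if there are symptoms, such as chest pain, shortness of breath or neurological symptoms". Section 5.2.4 adds extra blood pressure readings on signs of hypertension, and allows extra temperature readings once a participant is more than 1°C above Baseline.

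**The concern.** Short-lived rises in blood pressure and heart rate are an expected drug effect in this protocol (section 7.2.2). For such an effect, the basic descriptive safety question is how many participants ever went above a given level, and how far. A table of readings by timepoint describes each moment separately and does not link moments within a person.

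The measurement schedule sharpens this. Section 7.2.2 expects the rises to be over within six hours, so the later routine set falls at about the time they should have ended. The routine sets are about 4.5 hours apart, and the readings in between are those prompted by symptoms or signs. Those readings are likely to hold the peaks, yet the SAP is silent on their place in the table.

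At stake is whether a Phase 1/2 study meant to estimate safety can state a simple participant-level incidence for these effects.

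**Working it through.** Neither document states a figure for this table, so there is nothing to reproduce. The check is whether the participant-level count follows from the planned output.

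**Inputs**
- Participants dosed: 10 dyads × 2 = N = 20 (protocol section 6.2; both members receive MDMA).
- Routine post-dose sets per session: 2, at about 1.5 h (11:30 minus 10:00) and about 6 h (Table 5). I treat the end-of-session reading in section 5.1.2 and the six-hour reading in Table 5 as the same one. Counting them separately would only widen the ranges below.
- Sessions: 2. Routine post-dose timepoints: T = 2 × 2 = 4.
- Gap between routine sets: 6 − 1.5 = 4.5 h.

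**Bounds.** Let c be the number of participants above the cutoff at each timepoint, taken as equal across timepoints for simplicity. Everyone counted at one timepoint has exceeded at least once, so the ever-exceeded count is at least c. Nobody can be ever-exceeded on routine readings without adding at least 1 to the sum of the rows, so the count is at most min(N, T × c).

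- c = 1 (5% per row): 1 to min(20, 4) = 4 participants, 5% to 20%.
- c = 2 (10% per row): 2 to min(20, 8) = 8 participants, 10% to 40%.
- c = 3 (15% per row): 3 to min(20, 12) = 12 participants, 15% to 60%.

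The same table is therefore compatible with ever-exceeded counts that differ by up to a factor of 4. The values of c are assumed, since the documents give none. The bounds also assume that each row counts participants out of 20. The SAP's wording is about readings, which leaves even that open.

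**As-needed readings.** Two handlings fit the SAP's text:
- If they are given their own row, several readings from one symptomatic person could each be counted, on a denominator the SAP does not state. There would still be no ever-exceeded count.
- If they are left out of the table and are the only high readings in 0 to 3 people, every routine row shows 0/20 while 0 to 3 of 20 (0% to 15%) were above the limit at some time.

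**Cutoff.** The SAP refers to readings above a cutoff. The protocol's printed values are of other kinds: 140/90 mmHg as an eligibility and background figure (sections 4.2.2 and 7.2.2), and temperature rises from Baseline as action points (section 7.2.4, for example "If at any time the temperature rises more than 1.5°C above Baseline"). None is labelled an analysis cutoff, and there is no printed heart-rate limit to use.

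**The case against.** The strongest reply is that a reader may infer too much. Three inferences are tempting, and the documents do not support them.

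- **That as-needed readings are excluded from the table.** The SAP never limits the table to scheduled times, and Table 5 has a row for as-needed vital signs that a programmer could carry over. The SAP is silent on these readings; it does not order their omission.
- **That the study would hide or understate cardiovascular or temperature harm.** Adverse events are the SAP's primary safety measure. The protocol's definition (section 8.1) covers abnormal signs, and the SAP counts each subject once per preferred term at highest severity. Anything left out of the tables still goes to the data listings (SAP section 6.0), which can be read in full for 20 people. The protocol also describes the temperature rise as slight (section 7.2.4).
- **That the protocol sets a benchmark the table fails to meet.** Section 7.2.2 says: "In less than 5% of volunteers in Phase 1 studies, peak blood pressure values were higher than 140/90 mmHg". That is background on other studies. No comparison with it is planned, and a peak count here would not by itself be comparable, because the measurement frequency in those studies is not given.

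These replies stand against the stronger readings but do not close the gap. No numerical vital-sign value makes a reading an adverse event, and blood pressure rises are described as expected, so a symptomless rise need not be recorded as one. Listings give no incidence. The SAP already takes a worst-case or cumulative view for adverse events and the C-SSRS; vital signs are the exception.

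One further objection stands in full: a maximum partly reflects how often a person was measured. That has to be shown beside the result.

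**Conclusion.** The point holds as a specification gap in the vital-signs analysis. The cutoff has no stated value, the denominator and the handling of as-needed readings are undefined, and no participant-level maximum or ever-exceeded count is planned. The participant-level incidence cannot be derived from the planned table: in the illustration, 15% in every row fits 15% to 60% of participants.

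That range rests on assumed counts, on rows counting participants out of 20, and on four routine post-dose timepoints. The qualitative conclusion depends on none of these. It does not show that readings would be lost or harm concealed. Nor would the added table recover a symptomless peak that fell between readings and was never measured. The primary efficacy analysis is unaffected.

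**What to change.** In SAP section 6, under vital signs:

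1. Assign every post-dose reading, routine or as-needed, to the post-dose period of its session.
2. For systolic pressure, diastolic pressure, heart rate and temperature, report each participant's maximum post-dose value and maximum change from pre-dose, per session and overall, for the total sample and by PTSD+ and CSO.
3. Report, on the same layout, the number and percent of participants with any post-dose reading above each cutoff, with participants dosed as the denominator.
4. Have the sponsor state the value of each pre-determined cutoff. The protocol's 140/90 mmHg and its 1°C and 1.5°C rises may be used only as descriptive reporting categories. No change to monitoring or clinical management is implied.
5. Show the number of readings per participant alongside, so that maxima can be read against measurement frequency.
6. Keep the by-timepoint table as support, and state its denominator and how as-needed readings are placed in it.

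The cost is a few sentences of SAP text and one extra table from data already collected.
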